According to the 2013 update of the European League Against Rheumatism (EULAR) recommendations for the management of rheumatoid arthritis (RA), glucocorticoid (GC) withdrawal should be considered in patients reaching a target of remission or low disease activity to prevent or minimize the adverse effects of long-term GC therapy. While GCs are widely used in RA and GC withdrawal exposes RA patients to flare, joint destruction, withdrawal syndrome and adrenal insufficiency, there is an unmet need for an effective and safe GC withdrawal strategy to decrease these risks and increase the rate of effective GC withdrawal. Hydrocortisone replacement therapy has been proposed as a potential strategy to decrease the risk of GC withdrawal syndrome and adrenal insufficiency in patients subject to long-term GC therapy. We hypothesise that this strategy, which has never been investigated in RA, may increase the probability of GC withdrawal and decrease the risk of adverse events in RA patients who are candidates for GC withdrawal.

2) Study Design

This study is a national multicenter double-blind parallel arm, phase IV, controlled 1:1 randomized trial of superiority comparing two strategies of GC withdrawal in patients in remission or low disease activity:

- **Group 1:** tapering prednisone using a pre-defined schedule and hydrocortisone placebo (GC tapering group).
- **Group 2:** replacing prednisone with hydrocortisone and a prednisone placebo with a predefined schedule for tapering the prednisone placebo (hydrocortisone replacement group).

Randomization will be performed if DAS28 is lower than 3.2 after one month of a stable dose of prednisone 5 mg/day, and will be stratified on the center and the length of the GC duration before the beginning of the study.

STAR – Statistical Analysis Plan
V3, June 2023

Page 8 of 96

3) Primary Objective

To compare a prednisone tapering strategy to a hydrocortisone replacement strategy on the success rate of prednisone and hydrocortisone withdrawal at one year in RA patients in low disease activity or remission.

4) Secondary Objectives

1. To compare the proportion of patients who could withdraw from prednisone whatever the additional hydrocortisone associated treatment.
2. To compare the proportion of patients with acute adrenal insufficiency at one year between the two groups.
3. To compare the proportion of patients with biological adrenal insufficiency at one year between the two groups.

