- Hypotension.
- Biological abnormality such as hyponatremia, hyperkalemia, renal salt loss and hypoglycemia.

If an acute adrenal insufficiency is suspected, an extra visit will be performed in emergency and if the acute adrenal insufficiency is confirmed, the patient will be hospitalized to be treated at the choice of the investigator. If the serum cortisol dosage confirms clinical adrenal insufficiency, an open hydrocortisone therapy by hydrocortisone 20mg/d will be started and an appointment with the endocrinologist will be made. If the serum dosage does not confirm adrenal insufficiency, hydrocortisone will be stopped and other causes of the symptoms will be investigated. If no severe concomitant disease is found, the patient will be able to go back to her/his step of the protocol.

All clinical adrenal insufficiency reports will be reviewed by an independent committee to decide whether, according to the report, the diagnosis of clinical adrenal insufficiency can be validated and recorded for the study. This will be declared as a serious adverse event.

It is expected that less than 1% of patients in this study will experience clinical adrenal insufficiency.

3. Proportion of patients with biological adrenal insufficiency.

Two blood tests will be scheduled with a Synacthène® test at 4 and 7 months. A pathological Synacthène® test will be diagnosed if one hour after Synacthène®, serum cortisol is below 200 ng/mL or 600 nmol/L, or 20 µg/100 ml. In case of abnormal test at the latest Synacthène® test another Synacthène® test will be realized at M12.

4. Proportion of patients who needed a short rescue GC treatment during the protocol.
5. Proportion of patients who needed a GC intra-articular or peri-articular injection during the protocol related to the RA.
6. Proportion of patients with a flare confirmed by the clinician. In case of symptoms of flare, the patient will have an extra visit at her/his center. For DAS28 >3.2, a flare will be confirmed. A flare will be also diagnosed if the DAS28 is >3.2 at any scheduled visits.
7. The area under the curves of the self-administered Flare Assessment in Rheumatoid Arthritis (FLARE) questionnaire. FLARE is an approved self-assessment questionnaire that will be completed at each visit and in case of FLARE at home by the patient. The results are expressed as continuous data. The area under the curve of all the questionnaires will be the variable analyzed.

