34	Collection of consent (yes/no)	From the variable Date of signing of free and informed consent [CRF p9], the variable “Collection of consent” will take the value: " If yes : 
 • Consent signature date = not missing " Not if : 
 • Consent signature date = missing
35	Number of prednisone capsules consumed per level at M4 and M7	From the variables Prednisone bottle: Number of units reported and Prednisone bottle: Number of units given during the previous visit , the variable “ Number of prednisone capsules consumed at level 1 ” will take the value: Corresponding to the subtraction between: The number of units given and the number of units reported at level 1 [CRF p 45 and 90] The variables Number of prednisone capsules consumed at level 2/3/4/5/6 and Number of hydrocortisone consumed at level 1/2/3/4/5/6 will be derived using the same methods.
36	Total number of prednisone capsules consumed at M4 and M7	From the variables Number of prednisone capsules consumed at level 1 / 2 / 3 , the variable “ Total number of capsules consumed at M4” will correspond to the sum of all the variables mentioned (i.e. the sum of the number of capsules consumed at level 1, 2 and 3). Total Number variable of prednisone capsules consumed at M7 will be derived using the same methods using the variables Number of prednisone capsules consumed at level 1/2/3 . Variables Total number of hydrocortisone capsules consumed at M4 and Total number of hydrocortisone capsules consumed at M7 will be derived using the same methods.
37	Patient with pathological Synacthen test at M4 / M7 / M9 / M12 / VA1 / VA2 (yes/no)	Given the significant number of concordance problems between the variable “ Cortisol 60 minutes after stimulation with 0.25 mg of Synacthen® ” and the binary variable “ Is the Synacthen test considered pathological? ”, we have chosen to derive a variable which will allow us to reclassify patients with a pathological test or not, depending on the quantitative value of the variable “ Cortisol 60 minutes after stimulation with 0.25 mg of Synacthen® ”. This variable will be derived as follows:

STAR – Statistical Analysis Plan
V3, June 2023

Page 26 of 96

[figure not shown]
No.	VARIABLE NAME	DERIVATIONS

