If acute adrenal insufficiency is suspected, an additional visit will be performed as an emergency and if acute adrenal insufficiency is confirmed, the patient will be hospitalized for treatment at the discretion of the investigator. If the serum cortisol dosage confirms clinical adrenal insufficiency, open therapy with hydrocortisone 20 mg/day will be started and an appointment with the endocrinologist will be made. If the serum level does not confirm adrenal insufficiency, hydrocortisone will be stopped and other causes of the symptoms will be sought. If no serious concomitant illness is found, the patient can resume treatment. All reports of clinical adrenal insufficiency will be reviewed by an independent committee to decide whether, according to the report, the diagnosis of clinical adrenal insufficiency can be validated and recorded for the study. This deficiency will be reported as a serious adverse event.

It is anticipated that less than 1% of patients in this study will have clinical adrenal insufficiency.

The proportion of patients with acute adrenal insufficiency will be described in both groups. This result will be expressed as a percentage. We anticipate that less than 1% of patients included in this study will experience acute adrenal insufficiency and therefore no tests are planned for comparison.

For this analysis, the variable **“Acute adrenal insufficiency”** [CRF p111] will be described in the two groups.

STAR – Statistical Analysis Plan
V3, June 2023

Page 67 of 96

3) Proportion of patients with biological adrenal insufficiency at one year

Proportion of patients with biological adrenal insufficiency.

Two blood tests will be scheduled with a Synacthène® test at 4 and 7 months. A pathological Synacthène® test will be diagnosed if, one hour after Synacthène®, serum cortisol is below 200 ng/mL or 600 nmol/L, or 20 µg/100 ml. In the event of an abnormal test, at the latest, another Synacthène® test will be carried out at M12.

Variable name	Derivations

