
Presence of biological adrenal insufficiency at one year (yes/no)
	
From the variables “ Test performed (Synacthen test) (yes/no) ” at M12 [CRFp127], “ Is the Synacthen test considered pathological? (yes /no) ” to M12 [Derived variable], “ Has hydrocortisone treatment been received in addition to the protocol since the last consultation? » and “ Biological signs of chronic adrenal insufficiency ” [CRFp111], we define 2 modalities:
 
" If yes :
 
 • “ Test carried out (Synacthen test) ” = Yes • AND “ Is the Synacthen test considered pathological? » = Yes 
OR
 
 • “ Has hydrocortisone treatment been received in addition to the protocol since the last consultation? » = Yes • AND “ Biological signs of chronic adrenal insufficiency ” = Yes 
" Not if :
 
 • “ Test carried out (Synacthen test) ” = No • AND “ Has hydrocortisone treatment been received in addition to the protocol since the last consultation? » = No 
OR
 
 • OR if “ Test carried out (Synacthen test) ” = Yes • AND “ Is the Synacthen test considered pathological? » = No • AND “ Has hydrocortisone treatment been received in addition to the protocol since the last consultation? » = No

STAR – Statistical Analysis Plan
V3, June 2023

Page 68 of 96

4) Proportion of Patients Needing Supplemental Prednisone to Control Flares

Proportion of patients who required salvage GC treatment during the protocol.

To meet this secondary endpoint, we will use the Treatment Compliance Variables at M4, M7, M9, M12, Vadd 1 and Vadd2 which will be combined to create a new binary derived variable as presented below :

Variable name	Derivation

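### The one-year biological adrenal insufficiency variable codes untested, untreated patients as No whatever M4 or M7 showed, leaves two combinations unclassified and has no stated comparison method

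*SAP*

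**What the plan says.** Secondary Objectives, item 3, reads: "To compare the proportion of patients with biological adrenal insufficiency at one year between the two groups".

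The endpoint description (8) Endpoints, b. Secondary endpoints, item 3) sets the schedule: "Two blood tests will be scheduled with a Synacthène® test at 4 and 7 months". It gives a cut-off of 20 µg/100 mL one hour after stimulation, and adds: "In case of abnormal test at the latest Synacthène® test another Synacthène® test will be realized at M12". Section 3 of the secondary analyses repeats the schedule but words the retest differently: "In the event of an abnormal test, at the latest, another Synacthène® test will be carried out at M12".

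The derivation table in section 3 then defines "Presence of biological adrenal insufficiency at one year (yes/no)". It takes the test "at M12 [CRFp127]" and two items from the M12 treatment page: whether hydrocortisone was received on top of the protocol since the last consultation, and whether the reason was biological signs of chronic adrenal insufficiency (CRF p111). No M4 or M7 field enters. The section ends with this table.

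Variables of interest, no. 37, is "Patient with pathological Synacthen test at M4 / M7 / M9 / M12 / VA1 / VA2 (yes/no)". It recalculates the verdict from the 60-minute cortisol value, because that value and the verdict recorded in the CRF often disagreed. The Synacthen results at all visits are listed among the descriptive tables, which have one column per strategy.

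**The concern.** The text describes an endpoint measured at M4 and M7; the derivation builds one from M12 data, where testing depends on an earlier abnormal result. For a patient who was not retested, No therefore need not mean that a normal value was measured. It can even contradict the last measurement available.

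The SAP's rationale presents hydrocortisone replacement as a way to reduce withdrawal syndrome and adrenal insufficiency. Acute adrenal insufficiency is expected in fewer than 1% of patients and will not be tested, so endpoint 3 is the only adrenal endpoint that could support a between-arm comparison. If its No category contains patients with a pathological last test, the one-year proportions are too low. The difference between arms is also distorted if such patients are unevenly spread.

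**Working it through.** **No planned figure to reproduce.** The SAP states no rate, sample size or power for this endpoint. The check is of the derivation itself.

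**Step 1. Enumerate the derivation.** Inputs are the four items in the section 3 table, taking the M12 page as complete. The biological-signs item applies only if hydrocortisone was added; the verdict applies only if the test was done.

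| M12 test | Added hydrocortisone | Biological signs | Result |
|---|---|---|---|
| Not done | No | n/a | No |
| Not done | Yes | No | unclassified |
| Not done | Yes | Yes | Yes |
| Normal | No | n/a | No |
| Normal | Yes | No | unclassified |
| Normal | Yes | Yes | Yes |
| Pathological | No | n/a | Yes |
| Pathological | Yes | No | Yes |
| Pathological | Yes | Yes | Yes |

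Totals: 5 Yes + 2 No + 2 unclassified = 9. Two of the five Yes rows need no pathological M12 test.

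**Step 2. Who falls in the first row?** With no M12 test and no added hydrocortisone, the result is No for each of these:

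- Pathological at M7 on variable 37 but recorded as normal. If retesting followed the recorded verdict (an inference), no retest was triggered. The SAP expects such discordant patients: its Synacthen listing sets out to identify them, together with patients who did not receive the planned open-label hydrocortisone.
- Pathological at M7, but the M12 retest was missed.
- Pathological at M4 and normal at M7. The endpoint description triggers no retest, since the latest test was normal; the looser wording in section 3 leaves this open.
- Normal at M7, with a later deficit that was neither tested nor treated.

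In the first two groups, if no later test was done, No contradicts the last measured value. In the third it agrees with the last value. In the fourth nothing was measured.

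**Step 3. Comparison method.** Sections 1, 4, 5 and 6 of the secondary analyses state Chi2 with Fisher as fallback. Section 2 states that the result is described without a test. Section 3 states neither.

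**Step 4. Scale of one coding error.** With 51 patients per group (SAP, Sample size calculation), each patient wrongly coded No lowers that arm's proportion by 1/51 = 2.0 percentage points. As an assumed range, 1, 3 or 5 such patients in one arm and none in the other would shift the difference by 2.0, 5.9 (3/51) or 9.8 (5/51) points. The SAP does not say how many there are.

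**The case against.** The best defence is that M12 is the right time: both the objective and the section title refer to one year, and the derivation follows them. M4 and M7 are also awkward points for comparison. With randomization at M1, three months on each hydrocortisone step puts M4 and M7 at the ends of those steps (1 + 3 = 4; 4 + 3 = 7), so the arms are on different study treatment. Both arguments stand. They are reasons to keep the one-year variable and to treat M4 and M7 as supportive.

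A reader might infer more than the documents support:

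- *Only the M12 retest counts.* Added hydrocortisone with biological signs also gives Yes, and can carry an earlier abnormal result forward.
- *The M4 and M7 results are discarded or never set side by side.* They are described by arm. What is missing is a between-arm test or effect estimate.
- *Every patient is tested at M4 and M7.* This is a fair reading of the schedule, but it is not stated.
- *A deficit arising after M7 cannot be seen.* Tests can also be recorded at M9 and at additional visits, and treatment can reveal a deficit. It is missed only if neither tested nor treated with hydrocortisone.
- *The choice of M12 has a known cost in power.* On assumed rates, 51 per arm, with exact enumeration (two-sided 5%, Chi2 with Fisher fallback), 30% against 10% at M7 gives power 0.73. If 30%, 50% or 70% of cases recover by M12, the rates become 21% against 7%, 15% against 5% and 9% against 3%, with power 0.52, 0.31 and 0.10. These figures assume true recovery and no loss to follow-up. They describe a different question at M12 and do not measure miscoding.

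None of this answers the No rule, the unclassified rows or the absent method.

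**Conclusion.** The point holds as a defect in how the one-year variable is built and analysed. It does not show that one year is the wrong time. Three faults can be read directly from section 3: a No that ignores a pathological last test when the M12 test is absent and no hydrocortisone was added; two combinations with no classification; and no comparison method for an objective that calls for one. The lack of an effect estimate at M4 and M7 is a secondary gap.

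The direction of the No error is known: it understates insufficiency in whichever arm it occurs. Its size, and its effect on the difference between arms, cannot be derived from the SAP. The path through wrongly recorded verdicts assumes that sites retested on the recorded verdict; the missed-retest path needs no such assumption. The plan should be corrected before the analysis.

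**What to change.** Amend section 3 as follows:

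1. Keep the one-year variable, labelled as persistent biological adrenal insufficiency, and reconcile the two wordings of the retest condition.
2. Where the latest test was pathological on variable 37 and no M12 retest was done, code the patient as missing or as Yes, not as No. Fix the choice in advance and use the other coding as a sensitivity analysis.
3. Classify added hydrocortisone without biological signs, both when the M12 test is absent and when it is normal.
4. State Chi2, with Fisher as fallback, plus the difference in proportions and its 95% CI.
5. Add the same comparison of variable 37 at M4 and at M7 among patients tested. Call it supportive, and label it as adrenal response at that treatment step.

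The cost is a few lines in a signed amendment, using data already collected. The small downside is more secondary comparisons.

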You felt a greater need for help for several days in a row due to your polyarthritis

Synacthen test at M4, M7, M9, M12, VAdd 1, VAdd 2

- Test carried out (yes/no) [CRF p60, p85, p102, p127, p144, p155]
 - If Yes, specify:
 - Cortisol without stimulation (yes/no) [CRF p60, p85, p102, p127, p144, p155]
 - Test value (µg/100mL) [CRF p60, p85, p102, p127, p144, p155]
 - Cortisol 60 minutes after stimulation with 0.25 mg of Synacthène® (yes/no) [CRF p60, p85, p102, p127, p144, p155]
 - Test value (µg/100mL) [CRF p60, p85, p102, p127, p144, p155]
 - Is the Synacthen test considered pathological? (yes /no) [Derived variable]
 - If No, if cortisol at 60 minutes is normal and the patient is on open-label hydrocortisone, specify:
 - Maintenance of hydrocortisone, specify dosage (mg/day) (yes/no) [CRF p61, p86, p103, p128, p145, p156]
 - If Yes, specify why
 - Hydrocortisone withdrawal (yes/no) [CRF p61, p86, p103, p128, p145, p156]
 - Other, specify (yes/no) [CRF p61, p86, p103, p128, p145, p156]
 - Accuracy (listing) [CRF p61, p86, p103, p128, p145, p156]
 - If Yes, is the patient summoned again for the introduction of hydrocortisone in accordance with the protocol? (yes /no) [CRF p61, p86, p103, p128, p145, p156]
 -]If No, another attitude is adopted towards the results of a pathological Synacthen test, please specify:
 - The patient was already on Hydrocortisone before this visit (yes/no) [CRF p61, p86, p103, p128, p145, p156]
 - Other, specify (yes/no) [CRF p61, p86, p103, p128, p145, p156]
 - Accuracy (listing) [CRF p61, p86, p103, p128, p145, p156]

STAR – Statistical Analysis Plan
V3, June 2023

Page 54 of 96

We will identify discordant patients, that is to say, those having a pathological test after recalculation [derived variable] although they were declared as normal in the eCRF, as well as patients who did not receive a open-label hydrocortisone until the next visit as planned in the protocol (patients to be classified in the protocol deviation group).

STAR – Statistical Analysis Plan
V3, June 2023

Page 55 of 96

End of study sheet

- Follow-up duration variable] [Derived
- Did the patient complete the trial according to protocol? (yes /no) [CRF p157]
 - Specify the reason for premature termination:
 - Adverse event or serious adverse event (yes/no) [CRF p157]
 - Resumption of RA activity/prescription of long-term prednisone or prednisolone (yes/no) [CRF p157]
 - Patient's refusal to prosecute (yes/no) [CRF p157]

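### The one-year biological adrenal insufficiency rule gives 'No' regardless of earlier tests when there is no M12 test and no added hydrocortisone, and leaves two hydrocortisone-treated groups without a class

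*SAP*

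**What the plan says.** **When tests are done.** SAP section 8) b, secondary endpoint 3, schedules Synacthen tests at M4 and M7 and sets a 60-minute cortisol threshold. It adds: "In case of abnormal test at the latest Synacthène® test another Synacthène® test will be realized at M12". The endpoint section (secondary criteria, 3) repeats this as: "In the event of an abnormal test, at the latest, another Synacthène® test will be carried out at M12".

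**How the endpoint is derived.** In the same section, "Presence of biological adrenal insufficiency at one year (yes/no" uses four inputs:
- whether the M12 test was done ("Test performed (Synacthen test) (yes/no");
- whether it was pathological ("Is the Synacthen test considered pathological? (yes /no"), taken from the recalculated variable;
- whether hydrocortisone was added since the last consultation;
- whether the recorded reason was biological signs.

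'Yes' needs either a pathological M12 test, or added hydrocortisone for biological signs. 'No' needs no added hydrocortisone, together with an M12 test that was either not done or not pathological. There is no residual class and no missing class.

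**What is known about the tests.** Variable of interest no. 37 explains why test status is recalculated from the cortisol value: "Given the significant number of concordance problems between the variable" holding that value and the yes/no judgement in the CRF. The Synacthen listing says the analysts will identify "those having a pathological test after recalculation [derived variable] although they were declared as normal in the eCRF", and also patients who did not get the planned open-label hydrocortisone.

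**The concern.** At M12, 'test not done' covers two different kinds of patient. In one, the last test was normal and no retest was called for. In the other, the last test was pathological and no retest took place. If no added hydrocortisone is recorded, both become 'No'. For the second kind there is no evidence behind that value.

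The SAP itself foresees patients who could land there: those whose test is pathological on recalculation but was entered as normal, and those who did not receive the planned hydrocortisone. For such a patient the recalculation in variable no. 37 corrects the M7 result, but the correction does not reach the one-year endpoint.

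Separately, the rule is not exhaustive. A programmer who meets an unclassified patient has to choose a value, or drop the patient, with no pre-specified instruction. The proportion is one the trial sets out to compare between arms (secondary objective 3).

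**Working it through.** No stated figure has to be reproduced; the check is of the rule's logic.

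**Inputs.** From the endpoint derivation: M12 test done (T), M12 test pathological (P), added hydrocortisone (H), reason is biological signs (B). That H = Yes with B = No can occur follows from the separately recorded reasons. The M4 compliance list has acute insufficiency, clinical signs, stress/infection/surgery and other. The Modality 4 derivation confirms separate acute and clinical reasons at M12.

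**Rule as written.**
- Yes = (T and P) or (H and B)
- No = (not T and not H) or (T and not P and not H)

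**Every combination with complete data.**

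| M12 test | No added hydrocortisone | Added, biological signs | Added, other reason only |
|---|---|---|---|
| Not done | No | Yes | **no class** |
| Done, normal | No | Yes | **no class** |
| Done, pathological | Yes | Yes | Yes |

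Total: 5 Yes + 2 No + 2 without a class = 9. No cell is coded both ways.

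**Fault 1: top-left cell.** M4, M7, M9 and additional-visit results are not arguments of the rule. The cell is therefore 'No' whatever the latest earlier test showed.

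**Fault 2: the two cells marked 'no class'.** Other derivations in the SAP close this kind of gap. The long-term oral corticosteroid variable defaults to 'No', the flare variable accepts 'No or missing', and vitamin D supplementation (no. 29) has a 'Missing' class. This rule does none of these.

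**Missing inputs.** Allowing at least one input to be missing adds 16 combinations: 4 are 'Yes' and 12 have no class. One example is an M12 test done with no 60-minute value and no added hydrocortisone.

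**Scale.** Section 7 gives 51 randomized patients per group.
- One patient recoded from 'No' to 'Yes' moves an arm by 1/51 = 2.0 points.
- One 'No' patient set to missing changes the arm from y/51 to y/50, where y is the number of 'Yes'. The change is y/(50 × 51) = y/2550. As y is at most 50, this never exceeds 50/2550 = 2.0 points, and it is smaller when y is small.

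**The case against.** **The endpoint is status at one year.** Using M12 data is reasonable, and a pathological M7 result, five months older, does not establish status at M12. This stands. A reader might infer that the rule is shown to undercount adrenal insufficiency. The SAP does not support that, because function may have recovered. What follows is only that the status is unknown and that 'No' asserts more than is known. For the same reason, carrying the old result forward as 'Yes' should not be the main analysis.

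**Not every patient without a retest is affected.** A patient with a pathological last test who received added hydrocortisone for biological signs is already coded 'Yes'. The unsupported 'No' needs both no M12 test and no added hydrocortisone.

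**Who triggers the retest is not stated.** A reader might infer that the M12 test is done only when the site judged the latest test abnormal. The text says neither; it defines abnormal by a cortisol threshold and calls for a retest. That a patient entered as normal would go without a retest is plausible, but it is an inference.

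**Frequency is unknown.** Variable no. 37 reports discordance without direction, visit or count. Some of it may be tests entered as pathological with an adequate cortisol value, which do not create this fault. A reader might multiply up: five such patients in one arm would give 5/51 = 9.8 points. That count would be an assumption with nothing behind it in the SAP.

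**Handling of unclassified patients is not stated.** A reader might infer that they leave the denominator. The SAP does not say so; it leaves the matter open.

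**Partial mitigation.** The Synacthen listing describes recalculated results at every visit and flags discordant patients, so they would be visible. The endpoint value would still be unchanged. The endpoint section also names no statistical test, which limits the consequence.

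**Conclusion.** Both faults follow from the derivation as written, and nothing elsewhere in the SAP repairs them.

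1. With no M12 test and no added hydrocortisone, 'No' is assigned even when the latest earlier recalculated test was pathological. The value is unsupported; it is not shown to be false.
2. Two of nine complete-data combinations have no class: hydrocortisone for other reasons only, with the M12 test not done or normal.

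The number of patients involved and the direction of any bias are not known from the SAP. The figure of about 2 points per patient assumes 51 patients per arm and recoding from 'No' to 'Yes'. This is a secondary endpoint, and the primary endpoint does not use the variable. The derivation should be corrected, but the trial's main conclusion does not depend on it.

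**What to change.** Amend the derivation as follows.

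- **Yes:** keep both current branches (pathological M12 test; added hydrocortisone for biological signs). They take precedence over everything below.
- **No:** the M12 test was normal or, without an M12 test, the latest available recalculated test was normal; in either case with no hydrocortisone for biological signs.
- **Missing:** the latest available recalculated test was pathological and no M12 retest was done, or no test result exists.
- **Hydrocortisone for other reasons only:** class by the same latest-test rule. This fills the two empty cells.
- **Missing inputs:** state the value to be assigned when the 60-minute cortisol or the hydrocortisone entry is absent.
- **Sensitivity analysis:** count patients with a pathological last test and no M12 retest as 'Yes'.
- **Reporting:** give by arm the number retested at M12 and the number set to missing.

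The cost is a few lines of derivation code, one sensitivity table and a signed SAP amendment. All variables are already collected, and nothing in patient management changes.
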